### Determination of Polygenic risk Scores and Gene Testing

Blood samples were taken from all women as part of the original FH-Risk study protocol, from which DNA was extracted, or pre-existing DNA samples (also previously extracted from blood) were used.

### ***Genetic testing - Assay methods***

Blood samples were taken from all women as part of the original FH-Risk study protocol, from which DNA was extracted, or pre-existing DNA samples (also previously extracted from blood) were used. *BRCA1/2* mutation testing was carried out when clinically indicated (the prior probability of identifying a mutation must have met the threshold of *BRCA1/2* likelihood probability  $\geq 10\%$  in accordance with UK clinical guidance (NICE 2013), using the Manchester score, using DNA Sanger sequencing and multiple ligation-dependent probe amplification analysis of all exons and intron/exon boundaries and more recently next generation sequencing). Relatives of those identified with *BRCA1/2* mutations were offered cascade screening for the family-specific genetic mutation. All women were genotyped for 18 SNPs that have been shown to be associated with breast cancer risk in general European populations (FGFR2, CASP8, TOX3, MAP3K, 2q, CDKN2A, 10q22, COX11, NOTCH, 11q13, 10q21, SLC4A7, 6q25.1, 8q24, RAD51L1, LSP1, 5p12, 10q). In brief, multiplex genotyping was performed using Sequenom iPLEX Gold (Sequenom, San Diego, California, USA) and TaqMan assay (Life Technologies). Intra-plate duplicates and negative controls were included in all genotyping. Genotypes were verified by Scientific Data Systems (SDS) and MassARRAY TyperAnalyze. Since the study feedback in 2013-14 further analysis (see above) has been carried out to perform a SNP313 PRS. All samples have also been sequenced for mutations in a panel of 35 genes including 14 that confer at least a moderate risk of breast cancer (Dorling et al 2020). Results of gene mutations in a panel of 35 genes are already available for all women who took part in the FH-Risk study.

### **Statistical Analysis Plan**

The baseline anthropometric, familial and hormonal information from the FHRPC questionnaires will be entered into the breast cancer risk prediction models under consideration (TCv8 and CanRisk) and estimates of absolute 10 year and lifetime risk to age 80 risk obtained for each woman. The performance of the models will be compared in two ways; differences in prediction of individual risk and the change in category of risk (average, moderate and high) according to NICE guidelines. The follow-up period will be taken to be the time from initial referral and first clinic assessment with risk assessment to the most recent assessment or December 1st 2020, whichever is later

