### **Risk estimation models to be used to recalculate risk**

#### ***Calculation using Tyrer-Cuzick Version 8***

Phenotypic risk will be assessed using predicted remaining 10-year and lifetime risks to age 85 from the TC model V8 (Tyrer 2004; <http://www.ems-trials.org/riskevaluator/>). The following information from the original risk questionnaire collected before 2012 will be incorporated: age at baseline; first and second-degree relatives (age affected by breast and ovarian cancer or current age or age at death); age at first child, menarche and menopause; height and weight; and history of prior benign breast disease. Changes in these risk parameters will be assessed at subsequent clinical appointments and incorporated into the model.

Version 8 of the TC Model differs from V6 in that risk is estimated until the age of 85 (from 73 or 80 years) and because breast cancer risks have generally increased since V6 was developed (Tyrer et al., 2004). Thus, women will have in any case somewhat higher risks than previously given at their initial

appointment. However they still may end up with a lower risk estimate than originally given when MD and SNPs are taken into account (Brentnall et al., 2015).

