### ***Calculation using BOADICEA V – Can-Risk***

Collaborative work with the Cambridge team that have now produced a user-friendly risk algorithm called CanRisk from their BOADICEA programme, means we can now provide bespoke breast cancer 10-year and remaining lifetime risks especially for those who carry pathogenic variants in moderate risk genes CHEK2 and ATM that are not provided for in Tyrer-Cuzick model (Archer et al 2020). CanRisk includes the same inputs as Tyrer-Cuzick (above) but also includes additional genes. Women will be provided the CanRisk output instead of Tyrer-Cuzick when they carry a pathogenic variant in any of the high or moderate risk genes. Comparisons will also be made to identify discrepancies in 10-year risks that would mean women were in different risk categories.

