#### Primary endpoints:

- 10-year and lifetime breast cancer risk and the corresponding NICE risk categories for two risk prediction models: i) TCv8 and ii) BOADICEA v5.
- Risk scores from TCv8 and BOADICEA will be assessed using different model inputs: i) classical factors alone, ii) classical factors plus mammographic density (BIRADS) and iii) classical factors plus mammographic density plus SNPs.

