## 3. Analysis

The primary analysis will compare the risk categories and risk scores for the risk prediction models for women at entry to the clinic (or age 40) and at last follow-up in the clinic, and will compare the risk scores given by TCv8 and BOADICEA using different model inputs.

- i) **Change in risk categories** – NICE risk categories (average, moderate and high) will be compared by creating cross tabulations of risk categories at entry and at last follow-up – the number (and percentage) of women moving up and down risk categories will be

reported and the McNemar-Bowker test will be used to determine whether the change in risk categories is statistically significant between the two time points.

- ii) **Change in 10-year and lifetime risk scores** - change in continuous risk measures (10-year and lifetime risk estimates) will be estimated from TCv8 and BOADICEA risk prediction models. Normality and skewness of 10-year and lifetime breast cancer risk scores will be assessed. Where there is evidence of non-normality scores will be transformed. Scatterplots and correlation coefficients will be used to examine the relationship between 10-year and lifetime risk estimates at baseline and at latest follow-up.

Descriptive statistics will be used to report change in risk scores from time at entry to latest follow-up and will be compared using a paired t-test. Linear regression will be used to determine which risk factors (e.g. SNP313, MD) are associated with change in risk score.

- iii) **Comparison between risk models** - descriptive statistics will be used to report risk scores from TCv8 and the BOADICEA models and differences in risk scores compared. Models will be compared using a) classical risk factors alone, b) classical risk factors plus mammographic density, as measured by BIRADS, which can be included in both models and c) classical risk factors plus mammographic density and SNPs. Scatterplots and correlation coefficients will be used to examine the relationships between models and Bland-Altman plots used to show the agreement between the models.

Secondary analysis will focus on the comparison between differences in mammographic density measures and the relationship with risk scores using TCv8.

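### Lifetime risk, part of the primary endpoint, ends at age 80 for both models in the SAP but at age 85 for Tyrer-Cuzick v8 in the methods, and nothing says which governs

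*Combined protocol and SAP*

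**What the plan says.** All the text is in the combined protocol and SAP, section 3.1 unless stated.

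- **Statistical Analysis Plan, opening paragraph.** For TCv8 and CanRisk together, the plan has "estimates of absolute 10 year and lifetime risk to age 80 risk obtained for each woman".
- **Calculation using Tyrer-Cuzick Version 8.** "Phenotypic risk will be assessed using predicted remaining 10-year and lifetime risks to age 85 from the TC model V8". The section presents the later end age as a feature of the new version: "risk is estimated until the age of 85 (from 73 or 80 years" in V6. It adds that "women will have in any case somewhat higher risks than previously given" at the first appointment, citing the longer horizon together with a general rise in breast cancer risk. The background on the Tyrer-Cuzick model (section 1.2) also gives 85.
- **Calculation using BOADICEA V – Can-Risk.** The collaboration "means we can now provide bespoke breast cancer 10-year and remaining lifetime risks". No end age is given.
- **Primary endpoints.** "10-year and lifetime breast cancer risk and the corresponding NICE risk categories for two risk prediction models", again with no end age. "Risk scores from TCv8 and BOADICEA will be assessed using different model inputs: i) classical factors alone", then with density added, then with density and SNPs.
- **Primary objective ix and Analysis, item iii.** Lifetime risk is compared between the two models by score differences and correlations, with "Bland-Altman plots used to show the agreement between the models".

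**The concern.** Two parts of one document define the same primary quantity differently. An analyst who takes TCv8 to 85 from the methods and CanRisk to 80 from the SAP can point to text for each choice, yet would compare risks over different spans. The gap runs one way: TCv8 gains five years of incidence that CanRisk lacks. It would enter the mean difference, the Bland-Altman bias and the between-model category comparison, and nothing in the output would show that it came from the horizon.

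There is a second consequence even if a single age is used throughout. The NICE cut-offs are fixed at 17% and 30%, while cumulative risk rises with the end age. The choice of 80 or 85 therefore affects the counts in every lifetime category table, including entry versus last follow-up and the nested input steps.

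**Working it through.** **Step 1: the end ages side by side.**

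| Source | TCv8 | CanRisk |
|---|---|---|
| SAP, opening paragraph | 80 | 80 |
| Methods, model sections | 85 | not stated |
| Background, section 1.2 | 85 | not stated |
| Primary endpoints, objective ix, Analysis iii | not stated | not stated |

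Following the SAP for both gives a gap of 80 − 80 = 0 years. Following the methods for TCv8 and the SAP for CanRisk gives 85 − 80 = 5 years. No text says that TCv8 output is to be cut back to 80. No stated sample size or other figure in the plan depends on the end age, so there is nothing to reproduce.

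**Step 2: what five years could add.** The documents give no incidence at these ages. Assume a rate h of 0.2% to 1.0% per year from 80 to 85 and no competing mortality. With R the risk to age 80:

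risk to 85 = 1 − (1 − R) × exp(−5h)

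- R = 28%, h = 0.2%: 1 − 0.72 × 0.99005 = 28.72%, or +0.72 points.
- R = 28%, h = 1.0%: 1 − 0.72 × 0.95123 = 31.51%, or +3.51 points.
- R = 16%, h = 0.2%: 1 − 0.84 × 0.99005 = 16.84%, or +0.84 points.
- R = 16%, h = 1.0%: 1 − 0.84 × 0.95123 = 20.10%, or +4.10 points.

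**Step 3: who changes category on horizon alone.** The lowest age-80 risk that reaches a cut-off T by 85 is 1 − (1 − T) × exp(5h).

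| Cut-off | h = 0.2% | h = 1.0% |
|---|---|---|
| 30% | 29.3% | 26.4% |
| 17% | 16.2% | 12.7% |

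The rate needed to move from R to 30% is ln[(1 − R)/0.70]/5. From 28% it is 0.56% per year. From 25% it is 1.38% per year, outside the assumed range.

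Both cut-offs matter. At the lowest rate, a risk of 16.5% to age 80 becomes 1 − 0.835 × 0.99005 = 17.3% to age 85, so a fall from moderate to average would not be recorded. The pilot study in section 1.2 reports 53 of 106 women falling by at least one category and names moderate to low as one such move.

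**Step 4: a second assumption as a check.** With a constant hazard from starting age a, the age-80 risk equivalent to T at 85 is 1 − (1 − T)^((80 − a)/(85 − a)). For a = 40 this gives 15.3% for the 17% cut-off and 27.2% for the 30% cut-off. Over starting ages 25 to 60 the equivalents run from 15.7% down to 13.9%, and from 27.9% down to 24.8%. That places the affected women about 1 to 5 points below a cut-off, broadly in line with Step 3.

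**Step 5: previously given risks (primary objective viii).** The stored estimates came from modified Claus, whose end age is not stated, or from Tyrer-Cuzick, with V6 ending at 73 or 80. Against a new end age of 80 or 85, the V6 end point moves by 0 (80 to 80) to 12 (73 to 85) years. Remaining lifetime risk also starts later at a later visit: a woman who entered in 2000 to 2012 and is assessed in 2020 is 8 to 20 years older. Her span therefore changes by between 0 − 20 = −20 and 12 − 8 = +4 years. No single direction or point range follows for that comparison.

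**The case against.** The strongest reply is that the opening paragraph is the analysis plan itself: it names both models and one age, so the five-year gap needs an analyst to override it for TCv8 while obeying it for CanRisk. On that reading the SAP also supplies the end age that the CanRisk section omits. This is a fair reading, and if it is the intended one the between-model gap is zero. What stands is that the methods text is equally explicit, presents 85 as a property of the version to be used, and is never said to yield to the SAP.

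The CanRisk section also plans a check for discrepancies in 10-year risk that would change category. This narrows the exposure, because 10-year risk has no end-age problem. It does not remove it, since lifetime risk and its categories remain in the primary endpoints and objective ix.

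The size is wholly assumed, and at the low rate it is small. That stands, and allowing for competing mortality would reduce it further.

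Three stronger readings are tempting and not supported:

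- A reader might infer that the between-model comparison is certainly biased. The documents show an unresolved conflict, not which age will be used.
- A reader might infer that density and SNP effects are contaminated. The nested scores within one model have no horizon mismatch if one end age is used; only their category counts depend on which age that is.
- A reader might infer that change from previously given risk is inflated by a calculable amount. The TCv8 section discloses an upward tendency, but Step 5 shows that the net span can shorten at later visits. Analysis item ii also takes change from TCv8 and BOADICEA and specifies no subtraction of the stored figure, although the research abstract describes comparing given with re-estimated risk.

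**Conclusion.** The contradiction is real and sits in the definition of a primary endpoint, so it should be fixed. Confidence in the textual conflict is high; its numerical effect is unknown. The between-model horizon gap is 0 or 5 years depending on which text is followed. Under the assumed 0.2% to 1.0% per year with no competing mortality, five years add about 0.7 to 4.1 points to risks of 16% to 28%. Women within roughly 1 to 4 points below a NICE cut-off could then be classed one category higher. How many women lie there is not stated.

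If one end age is used for both models, the between-model mismatch disappears. Entry versus last follow-up and the nested steps also have no end-age mismatch, though their category counts still depend on the age chosen. Ten-year results are unaffected. For change from previously given risk, the supported conclusion is only that the raw change mixes horizon and model-version differences with the new risk factors.

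**What to change.** Reconcile the opening SAP paragraph with the TCv8 and CanRisk calculation sections. State one end age for lifetime risk, and apply it to both models in every between-model comparison and every lifetime category table. Confirm first that both tools can output risk to that age. If they cannot, lead the between-model comparison with 10-year risk and label the lifetime results as having different horizons.

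For primary objective viii, label any raw change from previously given risk as including horizon and model-version differences. Attribute change to density and SNPs only from the nested scores on one horizon.

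The cost is text edits in three places, a check of what each tool can output, possibly re-running model output, and a line of labelling in the report. No new data are needed.

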#### **1. Objectives**

Primary

- vii) To determine change in NICE categories of risk (average, moderate and high risk) when new risk factors are added to standard breast cancer risk models.

- viii) To explore how much new risk models (including MD, SNP313 and mutation testing) change risk estimates previously communicated to women in the FH-Risk study, between their first referral and their latest visit to the FHRPC
- ix) To compare 10-year and lifetime risk estimates given by Tyrer-Cuzick (v8) and the BOADICEA model (v5) (Can-Risk)

#### Secondary

- i) To compare the risk profiles for TCv8 for different measures of mammographic density (BIRADS, Volpara and predicted VAS) (BOADICEA V5 – CanRisk uses only the BIRADS to assess MD).
- ii) To determine the reproducibility and validity of two readers of BIRADS

## 2. Methods

Analysis will be based on those individuals who attend two risk appointments – at time of entry to the FHRPC clinic and at their latest FHRPC clinic appointment and who have corresponding risk scores.

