## **METHODS**

### **Risk recalculation**

Risk recalculation will be performed on all 954 consented FH-Risk women's data.

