### **Participants and recruitment**

Women who opted to have their updated breast cancer risk and attended a consultation in Part 1 will be approached for this part of the study. All these women will be eligible apart from those who took part in interviews in Part 2 and 3 and those who did not consent to hearing about future related studies. Approximately 330-350 women will be eligible from Part 1. Women will be invited to take part in this follow-on questionnaire study via post. They will receive an invite letter, PIS, consent form and paper questionnaire, together with a pre-paid returning envelope.

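### Part 1 uses one analysis set, women with two risk appointments, although risk is recalculated for all 954 and most of the comparisons need only one date

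*Combined protocol and SAP*

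**What the plan says.** Under 2. Methods, the Statistical Analysis Plan (SAP, within section 3.1) gives one rule for Part 1: "Analysis will be based on those individuals who attend two risk appointments", the first at entry to the clinic and the second "at their latest FHRPC clinic appointment and who have corresponding risk scores". No objective is exempted, no other analysis set is defined, and 'risk appointment' is not explained.

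Elsewhere section 3.1 covers the whole cohort. The Risk recalculation paragraph states: "Risk recalculation will be performed on all 954 consented" women. The opening paragraph of the SAP has 10-year and lifetime "risk obtained for each woman".

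Of the primary objectives (SAP, 1. Objectives), vii asks how NICE categories change "when new risk factors are added to standard breast cancer risk models". Objective viii asks how estimates change "between their first referral and their latest visit to the FHRPC". Objective ix compares TCv8 with BOADICEA. The primary endpoints add a ladder of inputs: "Risk scores from TCv8 and BOADICEA will be assessed using different model inputs", starting with classical factors, then adding BIRADS density, then SNPs. The secondary objectives compare three density measures within TCv8 and two BIRADS readers.

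**The concern.** A comparison of two models, or of one model with and without density and SNPs, is made within the same woman on the same date. A second appointment adds nothing to it. Requiring one can only remove women whose scores the study has already planned to produce.

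What is at stake is mainly which population the reclassification percentages describe, and secondarily their precision. Two routes to selection are possible:

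- **Length of follow-up.** Section 3.1 ties discharge to age and risk category, so whether a woman has a later appointment could depend on the variable being reclassified.
- **Opting in.** If the second appointment is the updated-risk consultation of section 3.2, women must accept an invitation and meet its criteria: age 25 to 60, no breast cancer and a clear mammogram. The Procedure in section 3.2 gives this reading some support, because consent there covers access to records so that risk can be calculated before that appointment.

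**Working it through.** Part 1 has no sample-size calculation, so there is no stated figure to reproduce. The check has three steps.

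**1. Dates needed for each comparison**

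| Item in the SAP | Comparison | Dates needed |
|---|---|---|
| Primary vii, as worded | same model, with and without new factors | 1 |
| Primary viii | first referral against latest visit | 2 |
| Primary ix | TCv8 against BOADICEA | 1 |
| Input ladder (primary endpoints) | three sets of inputs | 1 |
| Secondary i | three density measures in TCv8 | 1 |
| Secondary ii | BIRADS readers | 1; no risk appointment needed |

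Two of the three primary objectives and both secondary objectives do not need the rule. Under 3. Analysis, item i tests category change only as entry against last follow-up, so objective vii as worded has no same-date test. Item iii, the model comparison, names no second date.

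**2. Inputs available at entry**

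- Classical factors: a completed entry risk form is an inclusion criterion for recalculation (section 3.1).
- SNP313 and gene panel: section 3.1 says results already exist for all women.
- Density: mammograms are to be read as near as possible to first referral. The number with a readable image near entry is not stated.

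**3. Possible size of the loss**

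The number meeting the two-appointment rule is not given. The values below are assumptions about how the rule might be read.

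- Any last clinic visit counts: up to 954, no loss.
- Updated-risk consultation: about 380 to 400. Section 3.7 says "Approximately 330-350 women will be eligible from Part 1", after removing interviewees. Adding back up to 50 (20 in Part 2, 30 in Part 3) gives 330 + 50 = 380 and 350 + 50 = 400. This is not a count of attenders, because section 3.7 also removes an unstated number of women who did not agree to hear about further studies.
- Only women still in follow-up: about 271 (section 3.1, October 2020).

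Half-width of a 95% interval = 1.96 × √(p(1 − p)/n). I take p = 0.50, the share moving down in the pilot (53 of 106, section 1.2), so the numerator is 1.96 × 0.5 = 0.98.

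| n | Share of 954 | Half-width (points) |
|---|---|---|
| 954 | 100% | 0.98/√954 = 3.2 |
| 400 | 41.9% | 0.98/√400 = 4.9 |
| 380 | 39.8% | 0.98/√380 = 5.0 |
| 271 | 28.4% | 0.98/√271 = 6.0 |

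**The case against.** The strongest reply is that the rule may exclude almost nobody. The Methods sentence names clinic entry and the latest clinic appointment; it does not name the updated-risk consultation. Section 3.1 says all FH-Risk women had or have annual mammography, and it uses the last clinic mammogram for discharged women. The abstract (section 1.1) says risk at both times is estimated retrospectively. On that reading nearly every woman could have both dates without opting in to anything. This stands, and it means the loss cannot be established from the documents.

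A reader might go further and infer that the rule discards more than half the cohort, or that it restricts the analysis to cancer-free women aged 25 to 60. The documents do not support either. The age, cancer and mammogram criteria in section 3.2 govern invitation to a consultation, and no document links the 330–350 or the 271 to the Part 1 analysis set.

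It can also be said that 954 is unrealistic for rungs that use density. Section 3.1 reports that raw images needed for density processing were not retained, and Volpara requires raw digital files. This stands in part: 954 is a ceiling for classical factors and SNPs only. But the ladder uses BIRADS, which is read visually, and the documents do not tie that reading to the missing raw images.

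Finally, one paired set keeps denominators the same across tables, and item i of 3. Analysis does use two dates. Neither justifies requiring a second appointment for a same-date comparison. Common denominators can be had by repeating those tables in the paired set.

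**Conclusion.** The point holds as a mismatch between the analysis set and the objectives. The two-appointment rule suits objective viii. It is unnecessary for objective vii as worded, objective ix, the input ladder and both secondary objectives, and for these it can only remove usable women.

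The size of the effect is unknown, from no loss at all to roughly 60–70% of the cohort on the narrower assumed readings (554 of 954 removed at n = 400, 683 of 954 at n = 271). The matching half-width at a 50% rate runs from 3.2 to about 6.0 points. Selection on age, cancer status and a clear mammogram would arise only if 'risk appointment' means the opt-in consultation, which the SAP does not say. The change is worth making before analysis because it costs little and removes dependence on an undefined term.

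**What to change.** Replace the single rule in 2. Methods with an analysis set for each objective:

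- **Input ladder, TCv8 against BOADICEA, and density comparisons:** every woman with the required inputs at entry. This is up to 954 for classical factors and SNPs. For rungs and comparisons that use density, it is women with a readable mammogram near entry. Add a same-date category cross-tabulation so that objective vii is answered as worded.
- **BIRADS reader comparison:** all images read, with no appointment condition.
- **Entry-to-latest change (objective viii):** keep the two-appointment set.

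Define 'risk appointment', stating whether the last clinic visit of a discharged woman counts. Report how many women fall in and out of the paired set, tabulated by entry age, entry category and discharge status.

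The cost is mainly SAP wording, since recalculation for the whole cohort and density reading near first referral are already planned. The drawback is that denominators will differ between tables, so each table must state its own; the same-date tables can be repeated in the paired set if direct comparison is wanted.
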